3.0 Objectives

The overall goal of this trial is to produce evidence on the effectiveness of a proven, pragmatic lifestyle intervention targeted at modest, clinically meaningful weight loss and increased physical activity among Veterans with obesity. In this simple, pragmatic clinical trial (PCT), and with input from the National Center for Health Promotion and Disease Prevention (NCP), we focus on the intervention's reach and its effectiveness on weight loss and generic health-related quality of life (HRQoL). We will examine secondary aims that include physical activity, sedentary behavior, dietary intake, blood pressure, sleep quality and self-efficacy. With success framed in reach and effectiveness, this VA-based PCT tests a low-cost, low-resource, behavioral weight loss intervention previously shown to be effective in non-VA primary care settings.

3.1 Scope of Problem to be Addressed

- Obesity is common; ~1/3 of Veterans in VA integrated service network (VISN) 20 and beyond are obese.
- As a preventable health risk, obesity and sedentary lifestyle surpass the prevalence and adverse effects of tobacco smoking.
- The MOVE! Weight Management Program for Veterans (MOVE!), developed by NCP, produces modest weight loss among those who participate. However, participation is currently limited to <5% of eligible Veterans. NCP is seeking approaches that improve the reach of obesity programs to more Veterans.
- The Blueprint for Excellence prioritizes the need to improve timely and efficient access to proven effective therapies for all Veterans by overcoming diverse geographic and technology-based barriers to care.
- The medical facility-focused care delivery model that requires in-person visits to VA facilities (both medical centers and outpatient clinics) limits reach and access to care based on distance and staffing availability.
- Multiple medical conditions compete with obesity for recognition and treatment in primary care.

3.2 Challenge

- Improve access to lifestyle interventions using a patient-centered and population-based approach.
- Provide obesity services to a diverse Veteran population through a broad selection of modalities.
- Overcome barriers to MOVE!'s population health impact for Veterans highlighted by VISN 20 evaluation:1.
- Low reach: <5% of Veterans eligible for MOVE! have used the program. Reach was likely limited by a number of factors, including: Distance with ~50% of Veterans living >30 miles from a local VA medical center or community based outpatient clinic (CBOC); Provider or patient self-referral enrollment system leading to differential participation based on the frequency of exposure to healthcare providers; Selection biases of patients who already experienced complications of obesity

were more likely to participate in MOVE!, which limits its potential for population health management.

- Heterogeneous adoption: A 14-fold variation in program use between VA medical centers among MOVE! eligible patients due to limitations of available resources and competing demands.
- Modest effectiveness among users: In-person MOVE! sessions at a VA facility constrains program effectiveness. Among Veterans who used MOVE!, ~50% had only one program encounter resulting in small amounts of weight loss of 1.3 lb (95% CI, -2.6 to -0.02 lb) and 0.9 lb (95% CI, -2.0 to 0.1 lb) at 6 and 12 months, respectively. Participating in six or more sessions resulted in greater weight loss at 12 months (-3.7 lb; 95% CI, -5.1 to -2.3 lb). Additionally, 15% of MOVE! enrollees lost 5% or more body weight, while 11% gained more than 5% of body weight.²

3.3 Opportunity

- The Evaluation of Lifestyle Interventions to Treat Elevated Cardiometabolic Risk in Primary Care (E-LITE) compared two active interventions with each other and usual care.⁴² Adapted from the Diabetes Prevention Program (DPP) lifestyle intervention,²⁷ the two E-LITE interventions were designed for primary care delivery through coach-led, in-person groups or self-directed-video with the option of remote coach support.
- The self-directed intervention^{46,62} was effective, simple, pragmatic and comparable to the group-based intervention and superior to usual care (at 2 years: Mean [s.e.], -4.5 [0.9] kg; 44% with >5% weight loss). These results informed and were incorporated into the 2014 United States Preventive Services Task Force (USPSTF) guidelines for behavioral counseling for CVD prevention in primary care.⁵⁶
- We will implement the E-LITE self-directed intervention (now called DELITE) in a patient-level randomized PCT of 500 Veterans with obesity. Our specific aims are to test whether, compared with usual care (UC) controls, intervention participants have better outcomes, including:
 1. **Primary measures:** Greater weight loss and improved physical function through 12 months.
 2. **Secondary measures:** Improvements in sustained weight loss, physical function and activity, sedentary behavior, diet quality, blood pressure, sleep quality, self-efficacy, and reach of the program to participants with obesity through 24 months. Budget impact analyses to aide NCP in decision making about potential dissemination.

3.4 Impact

Effective, pragmatic obesity treatment will address the most common preventable cause of disease in VA, having high clinical and public health importance.

4.0 Resources and Personnel

[figure not shown]
All study personnel are listed in section 1.0, including their contact information. Also detailed in that section: affiliation, role in study, who will have access to protected health information, who will be recruiting, consenting, administering surveys and who will perform data analysis.

5.0 Study Procedures

5.1 Study Design

DELITE is a simple, two-arm PCT in which 500 Veterans with obesity will be randomized to usual care (UC) or UC plus the DELITE self-directed lifestyle intervention for 12 months. We will assess weight change from baseline via CDW over a 24-month period and self-report assessment at 12 and 24 months. We hypothesize that intervention participants will have more weight loss and greater improvements in self-reported physical function at 12 months relative to UC controls. The design is depicted in **Figure 5** and described below.

Figure 5. Overall study flow

5.2 Recruitment Methods

5.2.1 Enroll Veterans within the Pacific and Mountain Time zones:

This broad area includes urban, rural and very rural areas, while allowing the lifestyle coach to retain normal working hours.

5.2.2 Identify Eligible Participants through CDW:

Before we begin recruitment, we will refine our algorithms that we will apply to CDW data to identify potentially eligible participants within the past year and verify with chart review.

5.2.3 Screening for Index Weight/BMI:

Using CDW, we will identify Veterans who had a primary care visit with an eligible BMI (index weight), a weight measurement in the previous 12 months indicating obesity (to minimize spurious inclusion), and who are likely free of exclusionary conditions searchable in CDW. We will retain pertinent socio-economic, demographic, and healthcare utilization data on all individuals identified to inform our organizational partners about the potential reach of the program.

5.2.4 Oversampling:

We will oversample:

- Women – our goal is to enroll approximately 30% of the cohort being women;
- Minorities, if necessary, to have a balanced proportion of the cohort;
- At VA Puget Sound HCS/CBOC's for study staff to obtain in-person weights for approximately 50 participants should the study team determine it is necessary to validate clinic weight measurements.

5.2.5 Research Invitation:

Using patients identified through CDW, we will mail invitations to enough Veterans to enroll 500 Veterans with obesity. The invitation packet will contain:

- Invitation Letter;
- Information Sheet;
- Opt in/out Post Card;
- Copies of Baseline Surveys with optional postage-paid return envelope.

We will pursue the option of posting the packet on the HSR&D public website for easy access in the future.

Once we meet our randomization goal, we will inform participants who have opted-in but are not yet randomized that enrollment is closed.

5.3 Informed Consent and Randomization

5.3.1 Telephone Screen, Consent, and Baseline Assessment:

Version 2.1, updated 3/17/2021, VA Puget Sound IRB Protocol Template-Version: 12/2015 Page | 17

For those potential participants who do not return an opt-out postcard within 2 weeks (or who return the opt/in card), a research coordinator may telephone to:

- Describe study and answer questions.
- Assess eligibility, including potential exclusions for safety. (Section 5.4)
- Obtain consent under a waiver of documentation of written informed consent.
- Administer baseline surveys; or participant may complete paper copies and return via postage-paid mail.
- Baseline assessment must occur no more than twelve weeks after the date of the index weight.

5.3.2 Medical Clearance:

For individuals who consent at the telephone screen and have fulfilled safety requirements, study staff will send a secure email to the patient's primary care provider to inform them of their patient's participation and to alert us if there is any reason that their patient should not participate. If the primary care provider does not respond after four days, we will send a second email. If no response to the second email, we will send a third email informing the PCP that we will enroll the individual in three business day unless they contact us otherwise. We will inform interested participants if their provider responded that this intervention is not appropriate.

5.3.3 Randomization:

DELITE staff will perform stratified randomization into the usual care or intervention group at a ratio of 1:1 within strata defined by age (<65 vs. \geq 65), BMI (three categories: \geq 30 and <35 vs. \geq 35.0 and <40 vs. \geq 40.0 and <45), and population density (Rural vs. Urban). Randomization must occur no more than twelve weeks after the date of the index weight. We will notify participants of their randomization group via mail. The mailing will include a weight scale, water bottle with a DELITE logo for all participant and the intervention materials (DVDs, binder containing introduction/instructions and the GLB curriculum, scale, CalorieKing Fat & Carbohydrate Counter, and paper tracking booklets) for intervention participants.

5.3.4 Continuation of Usual Care:

All participants will continue to receive standard medical care from their usual providers. The study will not interfere with ongoing patient care, including provider or patient referral to MOVE! or other available weight loss interventions. To account for changes in medical practice and secular trends and to protect external validity, no participant will be restricted from seeking or instructed not to seek weight loss treatment once enrolled and will be included in the intent-to-treat analyses.

5.3.5 Intervention:

5.3.5.1 Evidence-based intervention goals:

Weight: The intervention is designed to achieve and maintain a weight loss of 5-10% of baseline body weight in a gradual stepwise fashion. This amount of weight loss is safe, feasible and associated with clinically significant reductions in the risk of diabetes and cardiovascular disease such as hypertension.^{27,63-65} To help achieve and maintain the weight goal, participants are advised to reduce their calorie intake by 500-1000 kcal/day, as recommended in adult obesity guidelines, including the recent VA DOD clinical practice guideline.⁶⁶ Participants will gradually achieve the calorie goals through portion control, choices of low-energy and nutrient-dense meals and snacks (e.g., whole fruit, vegetables, whole grains, and low-fat, non-sweetened dairy products), reduced consumption of refined and/or added carbohydrates/sugars, healthy food preparation techniques, and careful selection of restaurant items.

Physical Activity: The physical activity goal is to achieve and maintain a minimum of 150 minutes per week of moderate-intensity physical activity (such as brisk walking). This goal is consistent with the 2008 Physical Activity Guidelines for Americans,⁶⁷ and is deemed safe and attainable for most adults, including those with chronic health conditions. Participants will gradually and steadily increase daily walking with a goal of achieving 150 minutes of brisk walking per week by the end of the 12-week video program (**Table 2**). Participants may also choose to adopt regular activities of moderate intensity other than brisk walking.^{68,69} After attaining the

minimum goal of 150 minutes per week, participants may choose to be more active; or if participants reach the 150-minute goal but are not achieving the weight goal, they will be encouraged to further gradually increase to 60 minutes/day of moderate physical activity^{61,68,70} while continuing to work on dietary changes.

5.3.5.2 Intervention format, structure, and content.

Within two weeks of randomizing a participant to the intervention group, a DELITE lifestyle coach will call to confirm receipt of the intervention package, review the materials and instructions, confirm understanding, and address any questions.

The DELITE core curriculum consists of watching one ~25-minute GLB video session (see Table 2 for list of topics) each week for 12 weeks, and using a corresponding GLB handout. The GLB also includes additional “Physical Activity Resource” videos with a corresponding handout. Participants may watch the sessions on DVD or online through the University of Pittsburgh GLB training center. The lifestyle coach will instruct participants about how to use the MFP website or paper-tracking booklets, depending on preference, for self-monitoring which may include weight, food intake, physical activity, GLB materials used, and how to contact the lifestyle coaching via MFP secure messaging or phone if they have questions or would like guidance with the lifestyle program. A lifestyle coach will send standardized reminders through MFP secure messaging or via mail for participants who choose to use paper trackers. As recommended by guidelines, the main objective of the core curriculum is to facilitate gradual weight loss through successive and progressive changes in diet and physical activity and behavioral skills training.

Months 4-12 focus on continued self-directed/monitored gradual weight loss and maintenance, and use of additional GLB handouts. Participants will have access to a lifestyle coach via MFP secure messaging or telephone as desired for the 12 months of the intervention. The choice to engage with a lifestyle coach is strictly up to the participant and will occur as seldom or often as the participant chooses. Self-monitoring is key to success in behavioral weight-loss interventions.⁷¹ The lifestyle coach will continue to send standardized reminders throughout the 12 months of the interventions.

5.3.5.3 Intervention adherence.

Other than sending the standardized reminders (Section 5.3.5.2), DELITE will not use special strategies to maintain or improve participant adherence to the intervention.

5.4 Inclusion/Exclusion Criteria

DELITE uses inclusion and exclusion criteria (Table 4) aimed at ensuring each participant's safety and maximizing internal validity, including minimizing error associated with the primary outcomes, and preventing possible missing data.

Table 4. Eligibility criteria

Inclusion

- Primary care measured BMI ≥ 30 and $<45 \text{ kg/m}^2$ and BMI measured in prior week indicating obesity;
- Able to participate fully in all study protocol/procedures including informed consent;
- Access to DVD player or internet.

Exclusion

- Inability to speak, read, or understand English;
- Participating in active weight loss intervention including use of prescription weight-loss medications in the past 3 months, current participation in group or individual weight loss programs provided by trained personnel, had/have plans for bariatric surgery during the study period;
- Expected weight loss because of alternate explanations, such as from illness;
- High variability in weight due to fluctuations in volume status (ascites – liver disease, chronic heart failure);
- Safety and/or adherence concerns due to severe physical or mental health issues or life expectancy <24 months;

- Pregnant, lactating, or planning to become pregnant during the study period;
- Participation in other intervention studies.

5.5 Study Evaluations

Table 5 shows the study measures and data collection schedule. We will send self-administered questionnaires to participants via mail with the option to complete and return by postage-paid mail. If the participant does not return the questionnaires by mail within two weeks, we may send a reminder letter or a study coordinator may attempt to administer them by telephone. To improve retention and the likelihood that participants will complete the follow-up evaluations, we will send a letter reminding them of their participation in the study at around the 4th, 8th, 16th, and 20th month after randomization.

5.5.1 Baseline Variables and Co-variates:

We will collect baseline variables and co-variates from CDW to the extent possible, and supplement with participant self-report surveys, MFP logs, and/or paper trackers.

5.5.2 Outcomes:

• Weight:

- For all participants, we will extract all outpatient-based weight measurements from CDW starting with 12 months prior index date through 27 months of follow up. For participants without a CDW weight:
 - We may include a reminder with the outcomes surveys to visit their primary care clinic to be weighed if a clinic visit is safe and feasible.
 - During times when a clinic visit is not feasible (i.e., currently, during SARS-CoV-2 pandemic), we will include a self-weight form with the outcomes surveys for those without a CDW weight to weigh themselves at home. The self-weight survey and instructions for self-weighing will be in lieu of a reminder to visit their clinic to avoid encouraging participants seeking medical care unnecessarily, given public health guidance to avoid healthcare settings for anything other than urgent care requiring in-person contact. All participants without a 24-month CDW outcome will be asked to self-weigh using a letter asking the participant to weigh themselves using the scales provided by DELITE at baseline. The mailing will include instructions about how to make the measurement (e.g., light indoor clothing, no shoes or other heavy items), a form to record the weight, and a postage-paid return envelope. If we do not receive a mailed response from participants within 2-weeks, a study coordinator may call the participant and ask them to weigh themselves and report the weight over the telephone.
 - A participant's primary outcome weight will be the one measured closest to 12 months AND between nine and 15 months, in a primary care-based clinic, and extracted from CDW. We will consider other weights as secondary outcomes.
- To validate clinic weights, we asked some VA Puget Sound HCS/CBOC participants to visit the Seattle or American Lake campus for an in-person weight collected by study staff. We coordinated those visits with an existing clinic visit to have a clinic-based weight for comparison. If the scheduled visit is in a non-primary care clinic, we may ask the participant if we may accompany them to primary care for a weight check. If primary care does not enter the weight into CPRS, [name] may do so. We have completed this process as of early 2020 and won't add it again, given the pandemic.

- Generic health status: Assessed using the SF-12⁵⁵ at 12 months as a primary outcome and at 24 months as a secondary outcome. The SF-12 has been extensively tested and shown to be valid, reliable and responsive to change.
- Reach: We selected the most relevant measure for the present trial from the well-established RE-AIM framework⁷²: "reach," defined as the "number, proportion, and representativeness of individuals willing to participate in a given intervention." First, we will estimate the proportion of those eligible who agreed to participate, with total recruitment letters sent, and total eligibility screenings conducted as denominators.

Second, we will capture “representativeness” by comparing participants’ demographic characteristics to the VA patient population and to those who were eligible for the study.

- Physical activity: 7-item International Physical Activity Questionnaire (short IPAQ) which evaluates weekly walking, vigorous and moderate-intensity activity.⁷³
- Dietary quality/self-efficacy: Starting the Conversation⁷⁴ questionnaire with items pertaining to fat, fruit and vegetable intake, and sugar intake, as well as diet self-efficacy measures.⁷⁵
- Sleep-Related Disturbance and Impairment: 4-item sleep disturbance and 8-item sleep-related impairment scales from the NIH PROMIS measures.⁷⁶
- Blood pressure: diastolic and systolic values from 12 months prior index date to 27 months follow-up will be obtained from the CDW.
- Blood sugar levels: HbA1c levels from 12 months prior index date to 27 months follow-up will be obtained from CDW
- Other weight loss interventions: We will monitor through CDW data extraction for participation in MOVE! and by patient report for participation in programs outside VA, and we will control for such use in secondary analysis.
- Engagement of participants to the intervention will be assessed by: Through MFP and/or mailed survey:
 - Number of GLB sessions viewed, modality used (DVD vs. online), and use of handouts;
 - Number and topic of contacts with lifestyle coaches.
- Cost: We will conduct a budget impact analysis and determine implementation costs using VA Managerial Cost Account (MCA) System.

Table 5. Measures and timing of data collection.

Variable	Potential source of data	12 months prior	3 months Baseline	12 months	24 months
Program reach, baseline characteristics, and covariates					
Height	CDW		x		
Comorbidities	CDW/self-report	x	x	x	x
Medications	CDW	x	x	x	x
Healthcare utilization	CDW	x	x	x	x
Distance from primary care clinic	CDW		x		
Demographics	CDW; Self-report		x		
Weight loss programs	CDW/self-report			x	x
Self-monitoring	Self-report			x	x
Outcome assessments					
Primary					
Weight	CDW (primary care-based measurement through 15 mos)		x		x
SF-12	Self-report		x	x	x
Secondary					
Weight	CDW (all outpatient measurements* through 27 mos) or participant measured*	x	x	*x	x
Physical activity	Self-report		x	x	x
Dietary quality/self-efficacy	Self-report		x	x	x
Sleep disturbance / impairment	Self-report		x	x	x
Blood pressure	CDW	x	x	x	x
HbA1c	CDW	x	x	x	x
Other weight loss interventions	CDW/self-report	x	x	x	x
Engagement	Self-report			x	x
Percent accepting invitation	Invitation response		x		
Cost**	MCA				x
Reach	CDW/self-report/study tracking		x		
Adverse Event Surveillance					
Event form	CDW/Self-report			x	x

**other potential sources are Health Economics Resource Center (HERC), Non-VA Medical Care Files, VA/CMS Data for Research, and VHA Support Services Center (VSSC) via the following tools: Compensation & Pension Record Interchange (CAPRI), the Computerized Patient Record System (CPRS), VistAWeb, VINCI.

5.5.3 Participant Payment:

After the 24-month time point, we will compensate participants \$20 for completing the 12- or 24-month survey packets. We will pay participants an additional \$10 if they complete both packets, for a total possible of \$30.

Following payment submission, we may mail a letter notifying participants that participation is complete and payment has been submitted.

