Most Veterans who receive VA healthcare have obesity (41%) or are classified as overweight (37%), putting them at higher risk for multiple serious chronic health conditions. Providing evidence-based behavioral weight management programs to Veterans with obesity is a priority for the VA National Center for Health Promotion and Disease Prevention (NCP). While the VA NCP's MOVE! program - primarily delivered with in-person group visits - helps Veterans with obesity lose weight, its reach has been limited because of various barriers to care. Some Veterans may do better with a program they can complete from home at their own pace. In this trial, study investigators are examining the effectiveness among Veterans of a previously proven self-directed lifestyle intervention (called DVD Lifestyle Intervention (D-ELITE)) that targets modest, clinically meaningful weight loss over the course of a year using recorded video lessons (DVD or online streaming), written self-study aids, and optional lifestyle coaching. The study will compare participants randomly assigned to receive D-ELITE to those continuing in usual care on weight and self-reported general physical health status, one year after enrollment. Secondary outcomes include weight and general physical health status two years after enrollment; and obesity-related biometric measures (blood pressure and HbA1c) and self-report psychological and behavioral factors such as physical activity and sleep quality, at one- and two-years following enrollment.

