Veterans with obesity living in the western US were identified using the VA Corporate Data Warehouse (CDW), recruited to participate via mail and telephone, and randomly assigned to receive the study intervention or usual care alone. The study uses CDW to assess weight change and biometric outcomes. To assess self-report outcomes, participants completed questionnaires, by mail or telephone, at baseline and 12 months after randomization, and are currently completing 24-month follow-up questionnaires. The D-ELITE intervention focuses on gradual lifestyle behavior change aimed at improving eating habits and increasing physical activity. It encourages participants to gradually achieve and maintain a 5-10% loss of baseline body weight and at least 150 minutes of moderate-intensity physical activity, such as brisk walking, each week. The D-ELITE intervention program consists of watching one video, completing corresponding written self-guided learning materials, and tracking food intake and physical activity each week for the first 12 weeks, then working through 10 additional written handouts and continued food and activity tracking for the next nine months. Intervention participants have access to a lifestyle coach, as desired, for the full 12-month intervention period. In addition to patient outcomes, this study will examine the cost of delivering the intervention, information relevant to decision-makers and potential future dissemination. Evidence-based programs like this, which can be delivered remotely and with likely minimal resources required from the VA healthcare system, are greatly needed, especially now as the SARS-CoV-2 pandemic has required VA to rapidly transition to providing more remotely-delivered care.

Impact: The DELITE trial has potential to provide the evidence needed for deciding whether a low-cost, low-technology, self-directed program can be used to expand the treatment of obesity to a population-based level by improving access to obesity treatment regardless of Veteran place of residence.

List of Abbreviations

- Adverse event (AE)
- American Heart Association (AHA)
- Body mass index (BMI)
- Cardiovascular disease (CVD)
- Centers for Disease Control and Prevention (CDC)
- Centers for Medicare and Medicaid Services (CMS)
- Chronic obstructive Pulmonary Disease (COPD)
- Community based outpatient clinic (CBOC)
- Compensation & Pension Record Interchange (CAPRI)
- Computerized Patient Record System (CPRS)
- Confidence interval (CI)

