12-Month Outcome (Testing Method)	Significance Level	Power	Scenario Type	Mean Diff. (SD) Cohen's d	Sample Size (w/ 20% Attrition)	
					Per-Group	Total
Weight (ANOVA, with adjustment for baseline weight)	0.025	0.90	Mean Diff. = 7.7 SD = 50.0 Corr. b/w Baseline, 12-Mo. Measures = 0.97	7.7 (50.0) d = 0.154	78	156
			Conservative (25% Cohen's d reduction, Corr. = 0.95)	6.7 (57.7) d = 0.116	225	450
SF-12 PCS (t-test)	0.025	0.90	MCID = 5.00 SD = 8.88	5.00 (8.88) d = 0.563	100	200
			Conservative (25% Cohen's d reduction)	4.33 (10.25) d = 0.422	176	352

5.6.2 Retention:

As in other studies, we will carefully train and regularly review with staff best practices for retaining participants, including fully informed roles and responsibilities of staff and participants, and conveying an appreciation of participation and study identification. We will train staff to conduct effective informed consent to assure that participants fully understand the demands and nature of the study before they enroll. Coordinators will carefully review study requirements with participants, explain the concept of random assignment and what each treatment involves, and stress the importance of follow-up assessment even if they are not adhering to their assigned

treatment. We will use a database to systematically track participant activities, prompt the study team when action is required, and regularly produce quality control reports, all proven elements for participant retention.

5.6.3 Hypothesis Testing and Statistical Analyses:

We will use intention to treat (ITT) for all primary and secondary analyses. We will evaluate the dropout and missing data patterns for informative missingness⁸². To test for non-zero intervention effects on weight and SF-12 PCS, we will compare mean outcome between intervention and control groups at 12 month follow-up using the repeated-measures mixed-effects linear model:⁸³⁻⁸⁵

$$y_{ij} = \beta_0 + \beta_1(j) + \beta_2(\text{InterventionFollowUp}_{ij}) + \beta_3(\text{Age65Plus}_i) + \beta_4(\text{BMICat1}_i) + \beta_5(\text{BMICat2}_i) + \beta_6(\text{Urban}_i) + \alpha_i + e_{ij}$$

y_{ij} is the outcome (weight or SF-12 PCS) for patient i at baseline ($j = 0$) or 12-month follow-up ($j = 1$).

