Exploratory analyses of Aim 2's biometric, psychological, and behavioral outcomes will be examined using tests of mean difference between groups after adjusting for baseline measures and randomization covariates in linear or logistic models, drawing on models used for primary analyses. We also will examine effects among women, and have estimated—with the assumptions of 80% power, ICC of 0.9, and 150 women participants—that we will have power to detect a similarly-sized effect among women as in the prior E-LITE trial.⁶² Given these outcomes are exploratory and are not focused on hypothesis testing, adjustment for multiple comparisons will not be performed.⁸⁹ Rather, these analyses will report effect sizes and 95% confidence intervals, along with p-values, to aid with interpretation of clinical significance.

5.6.4 Budget Impact Analysis:

To assess the economic impact of the intervention, we will focus on budget impact analyses to establish a business case for future implementation if the intervention is successful. We will perform a budget impact analysis from the VA perspective using a 12-month intervention period. First, we will compare costs of care potentially associated with weight loss therapies between the intervention and control groups: VA nutrition and behavioral weight management healthcare visits and weight loss medication from the VA Managerial Cost Account (MCA) System and Health Economic Resource System (HERC).^{90,91} Second, we will estimate potential future D-ELITE implementation costs, combining estimated potential patients based on trial reach

findings with costs of identifying and recruiting patients; training lifestyle coaches; and activities performed by the lifestyle coach using detailed project logs, incorporating data on staff salaries.⁹²

5.6.5 Misclassification and Missing Data:

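### Does the unspecified promise to control for MOVE! and outside-programme use undermine the secondary results?

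*Combined protocol and SAP*

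**What the plan says.** Section 5.5.2, under other weight loss interventions, says MOVE! participation will be tracked through CDW and outside programmes by patient report, "and we will control for such use in secondary analysis". It names no variable, time window or outcome.

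Section 5.6.3 opens with "We will use intention to treat (ITT) for all primary and secondary analyses". The primary model for weight and SF-12 PCS contains time, intervention at follow-up, and the stratification variables (age, BMI category, urban or rural). For Aim 2, "biometric, psychological, and behavioral outcomes will be examined" by "tests of mean difference between groups after adjusting for baseline measures and randomization covariates in linear or logistic models", building on the primary models. The section calls these outcomes exploratory and reports effect sizes with 95% intervals. No model has a programme-use term. Section 5.6.4 uses weight-management visits and medication only to compare costs between arms.

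Section 2.2 says usual care includes MOVE!. Section 5.3.4 leaves everyone free to seek weight loss treatment once enrolled and keeps them in the intent-to-treat analyses. Section 5.4 excludes people currently in a supervised weight loss programme. Table 5 has two related rows: "Weight loss programs" among the covariates and "Other weight loss interventions" among the secondary outcomes.

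**The concern.** Programme use during the trial comes mainly after randomisation, because current users are excluded and later use is allowed. Assignment may itself change it: someone given DELITE may feel less need of MOVE!, or may become more engaged and seek it out. Conditioning on such a variable removes part of the comparison the trial was built to make, which is DELITE plus usual care against usual care as it stands. If motivation drives both programme use and weight loss, adjustment also adds bias.

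The wording leaves room for two readings. The term secondary analysis could mean a supplementary analysis, or it could mean the models for the secondary outcomes. The Abstract makes the second reading conceivable for 24-month weight and physical health, because it lists them apart from the biometric measures: "Secondary outcomes include weight and general physical health status two years after enrollment; and obesity-related biometric measures (blood pressure and HbA1c"). It separates them again in "The study uses CDW to assess weight change and biometric outcomes". One could then argue that the covariate list in section 5.6.3 does not cover 24-month weight and SF-12, and that the decision to adjust them for use could be taken after the data are seen.

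**Working it through.** **Which reading the text supports**

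- Section 3.3 lists sustained weight loss and physical function through 24 months among the secondary measures. That numbered list is the natural referent of Aim 2 in section 5.6.3.
- Section 5.6.3 says the Aim 2 models draw on the primary models. Neither set has a use term, so a 24-month weight or SF-12 model built this way would have none either.
- Where the protocol means outcomes it generally says secondary outcomes. Section 5.5.2 says secondary analysis, and section 5.3.4 has already placed later programme users in the intent-to-treat analyses.

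The supplementary reading is therefore the better supported one.

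**How far adjustment could move an estimate**

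The documents allow a calculation only for 12-month weight, so it serves as a yardstick.

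Inputs from the documents:

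- SD 50 lb and correlation 0.97, or 57.7 lb and 0.95 in the conservative row (section 5.6.1, Table 6)
- 20% attrition from 500 randomised 1:1, giving 250 × 0.8 = 200 analysed per arm
- MOVE! effect 0.9 lb at 12 months on average (section 2.1), or 3.7 lb with six or more sessions (section 3.2)
- MOVE! uptake below 5% (section 3.1); highest facility rate 16% (section 2.1)

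Assumed: the split of use by arm, and the strength of any unmeasured motivation.

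1. *The plan's own figure.* Residual SD = 50 × √(1 − 0.97²) = 12.16 lb. With two-sided alpha 0.025 and 90% power, n = 2 × [12.16 × (2.241 + 1.282) / 7.7]² = 61.9, so 62 per arm. Then 62 / 0.8 = 77.5, so 78. This matches section 5.6.1.

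2. *Precision.* Half-width of the 95% CI = 1.96 × 12.16 × √(2/200) = 2.38 lb. In the conservative row the residual SD is 57.7 × √(1 − 0.95²) = 18.02 lb and the half-width is 3.53 lb.

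3. *Shift without confounding.* Adjusted minus unadjusted effect = (programme weight loss) × (intervention use − control use). At 5% control and 2.5% intervention:
   - 0.9 × (0.025 − 0.05) = −0.023 lb
   - 3.7 × (0.025 − 0.05) = −0.093 lb

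   A negative shift makes DELITE look slightly better.

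4. *Shift with assumed motivation.* Motivation lowers weight by a set amount per SD and raises the log-odds of use by a set slope. The shift is minus the pooled within-arm coefficient for use, times the difference in use (intervention minus control).

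| Motivation assumed | Shift at 0.9 lb | Shift at 3.7 lb |
|---|---|---|
| none | −0.023 | −0.093 |
| 2 lb per SD, slope 0.5 | −0.047 | −0.117 |
| 4 lb per SD, slope 1 | −0.118 | −0.188 |

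   The sign reverses if the intervention arm uses more, and the shift is zero if use is equal. The largest entry is 0.188 / 2.38 = 8% of the half-width.

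5. *Gap needed for a shift of one tenth of the half-width (0.238 lb), without confounding.* 0.238 / 0.9 = 26.5 percentage points, or 0.238 / 3.7 = 6.4 points.

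**The case for a change.** The strongest case for acting is that the plan leaves open the variable, window, outcomes and status of an analysis that conditions on a post-randomisation variable, and that a few words in sections 5.5.2 and 5.6.3 would close the gap without new data. The small shift also rests on uptake figures from routine care, whereas trial volunteers may use programmes more. No rate is given for programmes outside VA. At an assumed 16% control and 8% intervention use, the model above gives 0.07 to 0.58 lb, and 0.58 lb is 24% of the 2.38 lb half-width. The yardstick is also 12-month weight, a primary outcome that the clause does not touch; the 24-month outcomes cannot be sized from the documents.

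Much of this stands as description. Section 5.6.3 is silent on the analysis, the adjusted quantity answers a different question, and the figures are illustrations rather than bounds. But a larger shift would appear only in an extra estimate set beside the intention-to-treat result, which is reported regardless.

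The available remedies add little. Restricting the secondary models to baseline measures and stratification variables repeats section 5.6.3. Programme use is already listed as a secondary outcome in Table 5, and section 5.6.4 already compares the cost of VA weight-management visits and medication between arms. Adjusting for use before randomisation would be harmless, but nothing in the plan depends on it.

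**Conclusion.** The clause names an analysis that section 5.6.3 does not describe, and that is all that remains of the concern. Followed as written, the primary results are unaffected and the Aim 2 models contain no use term, so the secondary results still compare DELITE plus usual care with usual care. A use-adjusted estimate would be a supplementary, exploratory figure, and an analyst would be expected to present it as such.

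At assumed use of 5% against 2.5%, it would differ from the unadjusted 12-month weight effect by about 0.02 to 0.19 lb, against a half-width of 2.4 lb (3.5 lb in the conservative scenario). That size depends on the assumed split and confounding and does not carry over to SF-12, blood pressure, HbA1c or 24-month weight. The conclusion does not depend on it: it rests on the supplementary reading, which sections 3.3, 5.3.4 and 5.6.3 support better than the alternative suggested by the Abstract. This is a gap that analysts can fill sensibly, with no material gain from rewriting the plan.
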